### **Number of subjects developed ARDS**

Berlin criteria for ARDS will be assessed on Day 1, 5, 15, and 29. The presence of ARDS and the degree of ARDS by Berlin criteria (Mild, Moderate, Severe) will be tabulated by treatment group at each visit.

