Approximately 100 subjects will be randomized (1:1) with an interim analysis after 50 subjects (approximately 25 per group). There will be no interruption in study conduct during interim analysis as this simply represents sponsor safety due diligence during the COVID-19 pandemic. Interim Futility Analysis: An interim futility analysis will be conducted to assess whether the trial will be terminated due to lack of efficacy (futility) based on all available data assessable for the primary endpoint and key secondary efficacy endpoints.

All subjects will be followed daily through Day 10 (note: for Day 6 through Day 10, this stipulation is for as long as subjects are hospitalized). After Day 6, if subjects are discharged from the hospital, evaluations at Day 15 and 29 are required. Berlin criteria for ARDS ([Appendix 3](#)) will be assessed on Day 1, 5, 15, and 29. Subjects remaining hospitalized will be followed daily through Day 29. Phone Checks will occur at Day 60 and Day 90 for vital status (living or deceased), any hospital re-admissions or serious/non-serious adverse events after the Day 29 Final Clinic Visit. Details are provided in [Appendix 1](#) (Schedule of Study Procedures). Clinical status will be evaluated for all hospitalized subjects daily with vital signs, Ordinal Scale (7 categories analogous to Cao et al. 2020), and NEWS at Screening/Baseline and during Liquid Alpha₁-PI (Human) plus SMT or placebo plus SMT treatment and during Follow-up. The NEWS calculation is delineated in [Appendix 2](#) and can be calculated using the on-line web tool at <https://www.mdcalc.com/national-early-warning-score-news>.

For all subjects, all laboratory samples must be drawn prior to infusion of Placebo/Liquid Alpha₁-PI (Human), if laboratory assessments are required for a day in which Placebo/Liquid Alpha₁-PI (Human) is being infused.

Respiratory samples for quantitative measurement of SARS-CoV-2 viral load by NAT or PCR (real-time RT-PCR) will be obtained on Day 1, and subsequently on Day 5± 1 day, Day 15± 1 day, and Day 29 ± 1 day (obtained via nasopharyngeal swab). The results of these samples are not necessary for continuing on study. Similarly, blood samples for quantitative measurement of

GRIFOLS Bioscience Industrial Group	Number	BIG-CL-PRT-000019	Version	6.0	Status	Effective	Effective Date	08-Dec-2021

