5.2 Exclusion Criteria

A subject meeting any of the following exclusion criteria is NOT eligible for participation in the study.

1. Subjects requiring invasive mechanical ventilation or ICU admission or with PaO₂/FIO₂ \leq 150 mm Hg (i.e., arterial oxygen in mm Hg divided by fraction inspired oxygen concentration [e.g., 0.21 for room air])
2. Clinical evidence of any significant acute or chronic disease that, in the opinion of the investigator, may place the subject at undue medical risk.

GRIFOLS Bioscience Industrial Group	Number	BIG-CL-PRT-000019	Version	6.0	Status	Effective	Effective Date	08-Dec-2021	Page	44 of 94
	GC2006 -A Multicenter, Randomized, Open-label, Parallel Group Pilot Study to Evaluate the Safety and Efficacy of Prolastin®-C Liquid plus Standard Medical Treatment (SMT) versus SMT alone in Hospitalized Subjects with COVID-19									
3. The subject has had a known serious anaphylactic reaction to blood, any blood-derived or plasma product, or known Selective IgA Deficiency with anti-IgA antibodies.										
4. A medical condition in which the infusion of additional fluid is contraindicated (e.g., decompensated congestive heart failure or renal failure with fluid overload). This includes currently uncontrolled congestive heart failure New York Heart Association Class III or IV stage heart failure.										
5. Shock that is unresponsive to fluid challenge and/or multiple vasopressors and accompanied by multiorgan failure considered not able to be reversed by the Principal Investigator										
6. Known alpha-1 antitrypsin deficiency for which the subject is already receiving alpha1-proteinase inhibitor augmentation therapy										
7. Women who are pregnant or breastfeeding. Female subjects of child-bearing potential must have a negative test for pregnancy blood or urine human chorionic gonadotropin (HCG)-based assay at Screening/Baseline Visit.										
8. Subjects for whom there is limitation of therapeutic effort such as “Do not resuscitate” status Note: If the decision is made not to apply treatments or therapeutic procedures that will provide little benefit for the suffering or agony the subject is experiencing, such a subject would not be appropriate for participation in this study and should be excluded.										
9. Currently participating in another interventional clinical trial with investigational medical product or device										

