7.1.2 Secondary Efficacy Variables

The secondary efficacy variables include:

- Assessment of Clinical Severity: Change in NEWS from baseline (Day 1 through Day 29)
The NEWS has demonstrated an ability to discriminate patients at risk of poor outcomes. This score is based on 7 clinical parameters (respiration rate, oxygen saturation, any supplemental oxygen, temperature, systolic blood pressure, heart rate, level of consciousness [Alert, Voice, Pain, Unresponsive]) <https://www.mdcalc.com/national-early-warning-score-news> (Appendix 2)
- Time to clinical response: NEWS ≤ 2 maintained for 24 hours, Day 1 through Day 29
- Time to hospital discharge: defined as duration of hospitalization from Day 1 through Day 29
- If admitted to ICU post randomization: Duration of ICU stay through Day 29
- Duration of any oxygen use Day 1 through Day 29
- If requiring mechanical ventilation post randomization: Duration mechanical ventilation through Day 29
- Absolute value and mean change from baseline in the Ordinal scale Day 1 through Day 29

The Ordinal scale is as follows:

- 1) Death;
- 2) Hospitalized, on invasive mechanical ventilation or extracorporeal membrane oxygenation (ECMO);
- 3) Hospitalized, on non-invasive ventilation or high flow oxygen devices;
- 4) Hospitalized, requiring supplemental oxygen;
- 5) Hospitalized, not requiring supplemental oxygen;
- 6) Not hospitalized, limitation on activities;
- 7) Not hospitalized, no limitations on activities.

- Proportion (percentage) of subjects in each severity category of the 7-point Ordinal scale at Day 15 and Day 29

GRIFOLS Bioscience Industrial Group	Number	BIG-CL-PRT-000019	Version	6.0	Status	Effective	Effective Date	08-Dec-2021
	GC2006 -A Multicenter, Randomized, Open-label, Parallel Group Pilot Study to Evaluate the Safety and Efficacy of Prolastin®-CLiquid plus Standard Medical Treatment (SMT) versus SMT alone in Hospitalized Subjects with						Page	50 of 94

- Time to sustained normalization of temperature and proportion of subjects with normalization of fever at all time points, defined as temperature $< 36.6^{\circ}\text{C}$ armpit, $< 37.2^{\circ}\text{C}$ oral, or $< 37.8^{\circ}\text{C}$ rectal sustained for at least 24 hours
- Number of subjects who develop ARDS through Day 29 ([Appendix 3](#))
- Length of time to clinical progression through Day 29 (defined as the time to death, mechanical ventilation, or ICU admission)

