7.2.2 Screening/Baseline and Randomized Treatment (Day 1)

All required screening and baseline (pre-infusion Day 1) procedures/assessments will be performed prior to administration of the blinded study drug infusion.

Assessments include the following:

- Informed consent
- Inclusion/exclusion criteria
- Pregnancy test for females of child-bearing potential
- Record demography, (including age [year of birth], gender, race, and ethnicity) disease characteristics (date of exposure, date of onset)
- Ordinal Scale assessment
- National Early Warning Score (NEWS) ([Appendix 2](#))
- Record clinical features key symptoms: fever, cough, shortness of breath, fatigue, myalgia etc.
- Vital signs (temperature, systolic and diastolic blood pressure, pulse, respiratory rate)
- Weight
- Record result of historical SARS-CoV-2 PCR (qualitative RT-PCR) or NAT or other commercial or public health assay approved by regulatory authorities as a diagnostic test for COVID-19 in any specimen during the current hospital admission OR 96 hours prior to the hospital admission date and prior to randomization (the SARS-CoV-2 test results must be performed by a hospital laboratory and the documentation available) (eligibility criterion)
- If subject is receiving oxygen, record any supplemental oxygen administration (type, %, flow start/end date/time)
- Record hospital admission date
- Record oxygen saturation (specify on or off oxygen supplementation)
- Respiratory sample for quantitative measurement of SARS-CoV-2 viral load by NAT or PCR (real-time RT-PCR) (obtained via nasopharyngeal swab)

GRIFOLS Bioscience Industrial Group	Number	BIG-CL-PRT-000019	Version	6.0	Status	Effective	Effective Date	08-Dec-2021
	GC2006 -A Multicenter, Randomized, Open-label, Parallel Group Pilot Study to Evaluate the Safety and Efficacy of Prolastin®-CL Liquid plus Standard Medical Treatment (SMT) versus SMT alone in Hospitalized Subjects with						Page	52 of 94

- Sample for quantitative measurement of IgM and IgG antibodies to SARS-CoV-2 by enzyme linked immunosorbent assay (ELISA), Indirect Fluorescent Antibody (IFA), or another assay methodology (if antibodies cannot be determined at the site store *serum* samples frozen at -70°C for later analysis at an external lab)
- Serum Chemistry (creatinine, albumin, alanine aminotransferase [ALT], total bilirubin, lactate dehydrogenase [LDH])
- Calculate eGFR using the Cockcroft-Gault formula.

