Appendix 3 Acute Respiratory Distress Syndrome (ARDS) Berlin Definition

The Berlin Definition of Acute Respiratory Distress Syndrome is summarized in the table below. Timing is usually within 1 week of a known clinical insult or new or worsening respiratory symptoms.

Number	BIG-CL-PRT-000019	Version	6.0	Status	Effective	Effective Date	08-Dec-2021	Page	87 of 94
GC2006 -A Multicenter, Randomized, Open-label, Parallel Group Pilot Study to Evaluate the Safety and Efficacy of Prolastin®-CL Liquid plus Standard Medical Treatment (SMT) versus SMT alone in Hospitalized Subjects with									
Chest imaging ^a									
Origin of edema									
Oxygenation ^b ,									

Abbreviations: CPAP, continuous positive airway pressure; FIO₂, fraction of inspired oxygen; PaO₂, partial pressure of arterial oxygen; PEEP, positive end-expiratory pressure.

a. Chest radiograph or computed tomography scan.

b. If altitude is higher than 1000 m, the correction factor should be calculated as follows: [PaO₂/FIO₂ X (barometric pressure/760)].

c. This may be delivered noninvasively in the mild acute respiratory distress syndrome group.

The following may be used for the Berlin criteria, **for patients who are Not on a ventilator and do not have a blood gas performed.** *Since the effect of positive end-expiratory pressure (PEEP) may modify the derivation of SaO₂ to SpO₂, please do Not use SpO₂ to apply Berlin criteria to patients while on a mechanical ventilator.*

Respiratory Thresholds Determined by Pulse Oximetry Measurement of O₂ Saturation (for patients Not on mechanical ventilation)

PaO ₂ /FiO ₂	Corresponding SpO ₂ /FiO ₂ Threshold
≥ 400	≥ 512
<400	<512
<300	<357
<200	<214
<100	<89

Derivation of SpO₂/FiO₂ values corresponding to PaO₂/FiO₂ ratios in the combined anesthesia and ARMA database* [*Data derived from 4728 matched SpO₂/FiO₂ and PaO₂/FiO₂ measurements from the combined anesthesia and ARMA database]

References

ARDS Definition Task Force. Acute Respiratory Distress Syndrome – The Berlin Definition. JAMA. 2012;307(23):2526-2533. Doi:10.1001/jama.2012.5669

GRIFOLS

Number	Version	Status	Effective	Effective Date	08-Dec-2021

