### 2.2.2 Secondary Efficacy Endpoints

The secondary efficacy endpoints include the following:

- Assessment of Clinical Severity: Change in NEWS from baseline (Day 1 through Day 29).  
The NEWS has demonstrated an ability to discriminate patients at risk of poor outcomes. This score is based on 7 clinical parameters (respiration rate, oxygen saturation, any supplemental oxygen, temperature, systolic blood pressure, heart rate, level of consciousness [Alert, Voice, Pain, Unresponsive]).
- Time to clinical response: NEWS  $\leq 2$  maintained for 24 hours, Day 1 through Day 29
- Time to hospital discharge: defined as duration of hospitalization from Day 1 through Day 29
- If admitted to ICU post randomization: Duration of ICU stay through Day 29
- Duration of any oxygen use Day 1 through Day 29
- If requiring mechanical ventilation post randomization: Duration mechanical ventilation through Day 29
- Absolute value and mean change from baseline in the Ordinal scale Day 1 through Day 29  
The Ordinal scale is as follows:
  - 1) Death;
  - 2) Hospitalized, on invasive mechanical ventilation or extracorporeal membrane oxygenation (ECMO);
  - 3) Hospitalized, on non-invasive ventilation or high flow oxygen devices;
  - 4) Hospitalized, requiring supplemental oxygen;
  - 5) Hospitalized, not requiring supplemental oxygen;
  - 6) Not hospitalized, limitation on activities;
  - 7) Not hospitalized, no limitations on activities.
- Proportion (percentage) of subjects in each severity category of the 7-point Ordinal scale at Day 15 and Day 29
- Time to sustained normalization of temperature and proportion of subjects with normalization of fever at all time points, defined as temperature  $<36.6$  °C armpit,  $<37.2$  °C oral, or  $<37.8$  °C rectal sustained for at least 24 hours
- Number of subjects who develop Acute Respiratory Distress Syndrome (ARDS) through

Day 29

- Length of time to clinical progression through Day 29 (defined as the time to death, mechanical ventilation, or ICU admission)

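### The ARDS endpoint counts subjects who newly develop ARDS through Day 29, but the SAP plans only presence and degree at each visit, which does not in general yield that count and has no between-group estimate

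*SAP*

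**What the plan says.** Protocol 7.1.2 lists the endpoint as "Number of subjects who develop ARDS through Day 29". SAP 2.2.2 has the same: "Number of subjects who develop Acute Respiratory Distress Syndrome (ARDS) through" Day 29. Either way it is one cumulative yes/no value per subject.

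On measurement, the SAP 6.2 paragraph states: "Berlin criteria for ARDS will be assessed on Day 1, 5, 15, and 29". Protocol 4.2 has the same days. Protocol 7.2.2 lists the Berlin assessment among the Day 1 items, under the rule "All required screening and baseline (pre-infusion Day 1) procedures/assessments will be performed prior to administration of the blinded study drug infusion". The Day 1 result is therefore a pre-treatment baseline.

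On analysis, the SAP 6.2 paragraph says that presence and degree (mild, moderate, severe) "will be tabulated by treatment group at each visit". It says nothing further. SAP 8.2 includes ARDS among the outcomes for the futility review and refers back to Sections 6.1 and 6.2 for methods.

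**The concern.** To develop ARDS through Day 29 means new onset at some time during follow-up. A visit table gives something else: how many subjects have ARDS on a given day. It mixes cases present at entry with new ones, lets a case that has resolved disappear from later columns, and does not show whether Day 15 cases are the Day 5 cases or different people. Subjects who die between assessments drop out of later columns unless a rule says otherwise.

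Following the SAP as written therefore produces a different quantity from the one the endpoint names. A count of new ARDS could still be derived from the data. The choices on Day 1 cases, deaths and missed assessments would then be made without a pre-specified rule, and possibly after unblinding.

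**Working it through.** The plan states no ARDS rate, effect size or power, so there is no figure to reproduce. All rates and counts below are assumptions.

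**1. Analyses in SAP 6.2, side by side**

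| Endpoint | Between-group method |
|---|---|
| NEWS change | MMRM |
| Time to clinical response | Log-rank |
| Time to discharge | Gray's test |
| Durations (hospital, ICU, oxygen, ventilation) | ANOVA |
| Ordinal scale | MMRM; proportional odds |
| Temperature normalization | Log-rank; chi-square with risk difference and exact CI |
| Clinical progression | Log-rank |
| ARDS | None; visit table only |

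Protocol 9.1 does not fill the gap. It names log-rank, ANCOVA/ANOVA and Wilcoxon methods for secondary endpoints, but nothing for a binary one. SAP 4.4 announces worst-case imputation for binary efficacy endpoints where applicable and defers the details to Section 6. The ARDS paragraph has none.

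**2. Does the visit table determine the endpoint?** Take n subjects in an arm with complete data, b with ARDS on Day 1, and p5, p15, p29 with ARDS later. The number of new cases lies between

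- lower = max(0, largest of p5, p15, p29 minus b), when the cases overlap as much as possible;
- upper = min(n − b, p5 + p15 + p29), when they do not overlap at all.

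With n = 50:

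| Day 1 | Days 5, 15, 29 | Lower | Upper | At risk (n − b) |
|---|---|---|---|---|
| 0 | 8, 6, 3 | 8 | 8 + 6 + 3 = 17 | 50 |
| 5 | 8, 6, 3 | 8 − 5 = 3 | 17 | 45 |
| 10 | 12, 8, 4 | 12 − 10 = 2 | 12 + 8 + 4 = 24 | 40 |

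The first row has no baseline ARDS and still leaves 8/50 = 16% to 17/50 = 34%. In the extreme, two arms with identical visit tables could differ by 18 percentage points in new ARDS. The third row runs from 2/40 = 5% to 24/40 = 60%.

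**3. Can ARDS be present on Day 1?** Protocol 5.2, exclusion 1, bars PaO2/FiO2 of 150 mm Hg or less, need for invasive ventilation and need for ICU. Appendix 3, for unventilated subjects without a blood gas, pairs PaO2/FiO2 below 300 with SpO2/FiO2 below 357. SpO2 of 94% on an assumed FiO2 of 0.28 gives 94/0.28 = 336. Oxygenation in that range is therefore compatible with entry. The ratio is only one part of the Berlin definition, which in Appendix 3 also covers timing, imaging and origin of edema. Baseline ARDS is possible, but its frequency cannot be judged from the documents.

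**4. What would a comparison deliver?** Approximate power of a two-sided 5% chi-square test with n per arm, event rates p and q, and mean rate m:

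Φ{ [ |p − q|√n − 1.96√(2m(1 − m)) ] / √(p(1 − p) + q(1 − q)) }

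For 20% versus 10% and n = 50: (0.707 − 0.990)/0.5 = −0.565, so power is 29%.

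| Rates | n = 50 | n = 40 |
|---|---|---|
| 20% vs 10% | 29% | 24% |
| 30% vs 15% | 43% | 36% |
| 40% vs 20% | 59% | 50% |
| 30% vs 10% | 71% | 61% |

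The n = 40 column shows an at-risk set after removing an assumed 10 baseline cases per arm.

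**The case against.** Four points can be made for the plan, and each limits how far the concern goes.

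- **The data are not lost.** A reader might infer that ARDS would be absent from the results. It would not: presence and degree are shown by arm at every scheduled assessment, and SAP 6 promises listings of efficacy data. What is missing is the cumulative count and any pre-specified estimate.
- **Prevalence need not dilute the effect.** A reader might infer that baseline cases hide a treatment benefit. Suppose 15 of 50 in each arm have ARDS on Day 1, and 20% versus 10% of the other 35 develop it (7 versus 3.5 expected). If every case persists, the table shows 22/50 = 44% versus 18.5/50 = 37%. Subtracting the Day 1 column returns 7 and 3.5, and the 7-point gap equals the true difference over all randomized subjects (14% versus 7%). Recovery fails when cases resolve, recur or drop out, and the SAP cannot assume that none do.
- **Futility does not turn on ARDS.** SAP 8.2 gives a formula only for conditional power on the primary endpoint. ARDS is one of eleven secondary items and has no threshold. What stands is that the unblinded team would see visit counts with no new-onset number beside them.
- **A test adds little here.** The trial is exploratory and has no power calculation, and Protocol 9.1 leaves method choice to the SAP. This argues for reporting an interval as the main result. It does not justify leaving the endpoint underived. The SAP 7 statement that there will be no formal testing covers safety only.

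**Conclusion.** The concern holds. The planned output is point prevalence, and the endpoint is cumulative new onset. The first does not in general determine the second, even with complete data and no ARDS at baseline (8 to 17 new cases in the assumed example). The size in this trial cannot be stated, because the documents give no ARDS rates and the calculations rest on assumed counts.

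The documents do not support saying that many subjects would enter with ARDS, or that the visit table must understate a treatment effect. The importance is moderate: one secondary endpoint in an exploratory phase 2 trial. It should be corrected before unblinding, because the Day 1, death and missing-data rules affect the result and none is written down.

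**What to change.** In SAP 6.2:

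- Define a per-subject indicator of new ARDS: none on Day 1, and Berlin criteria met at any later scheduled assessment through Day 29.
- Report the count and proportion per arm with Clopper-Pearson intervals, and the risk difference with exact unconditional CI and chi-square test, as SAP 6.2 does for temperature normalization.
- Present this over all randomized subjects, in keeping with the ITT rule in SAP 4.2 (subjects with Day 1 ARDS stay in the denominator and are not new cases), and also among those without ARDS on Day 1.
- Handle missed assessments in line with the worst-case approach in SAP 4.4. Show deaths in subjects with no ARDS recorded beforehand as a separate count, with a sensitivity analysis counting them as events.
- Keep the visit table as descriptive, and use the new count in the futility output.

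The cost is one more table and no new data. Power stays low, so the estimate and its interval are the main gain. ARDS that starts and resolves between Days 1, 5, 15 and 29 would still be missed, because the schedule does not look for it on other days.

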### **Time to clinical progression**

Clinical progression is defined as death, start of mechanical ventilation, or ICU admission through Day 29, whichever occurs first. The time to clinical progression will be estimated using the KM method. The KM estimates along with 95% CI, and survival curves will be provided. Based on the KM estimates, the probabilities of experiencing clinical progression and associated 95% CIs on Days 15 and 29 will be reported; in addition, the 25th 50th (median), and 75th percentiles of the time to clinical progression with associated 95% CIs will be provided, as data permit. The survival rates between treatment groups will be compared using Log-rank test. The p-value from Log-rank test will be presented.

## **6.3 Exploratory Efficacy Endpoints and Analyses**

- Change from baseline in quantitative SARS-CoV-2 viral load by NAT or PCR (RT-PCR) to Days 5±1, 15±1, and 29±1 will be summarized for each treatment group by visit.
- Change from baseline in quantitative anti- SARS-CoV-2 IgM and IgG antibodies to Days 5±1, 15±1, and 29±1 will be summarized for each treatment group by visit.
- The proportion of subjects with evidence of hyperinflammation on Days 1, 5, 15, and 29 will

be tabulated by treatment group. For this analysis, the denominator for calculating the proportion at each visit and within each treatment group will be the number of subjects with non-missing values for Lymphocyte counts AND for at least 2 of the following 4 lab parameters: Ferritin, LDH, D-Dimers, and C-reactive protein (i.e., the number of subjects for whom evidence of hyperinflammation could be assessed).

- Change from baseline in cytokine profile (IL-1 $\beta$ , IL-10, IL-6, IL-8 IL-2, interferon  $\gamma$ , and TNF- $\alpha$ ) to Days 5 $\pm$ 1, 15 $\pm$ 1, and 29 $\pm$ 1 will be summarized for each treatment group by visit.
- Change from baseline in levels of alpha 1-PI (AAT) activity and antigen to Days 8, 15, and 29 will be summarized for each treatment group by visit.

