The primary efficacy analysis will be carried out on the ITT population and repeated on the PP population (if different from the ITT population) by Fisher's exact test. Secondary and exploratory efficacy analyses will be analyzed by means of Kaplan-Meier survival estimates and curves and compared between treatment groups by means of the Log-rank test for time to event variables, analysis of covariance (ANCOVA) when adjusting for covariates, or analysis of variance (ANOVA) when without covariates for normally-distributed variables or Wilcoxon rank-sum test for non-normally-distributed variables. Detailed data handling and evaluation procedures and details of the interim review will be described in the Statistical Analysis Plan (SAP).

For the primary endpoint, if the value of the subject is missing, then a conservative imputation rule will be used such that the subject will be treated as having met the condition for the primary efficacy analysis. The choice of analysis method for primary, secondary and exploratory efficacy endpoints will be described in detail in the SAP which will be finalized and signed off before data analysis is performed.

The SAP may include exploratory analyses of various aspects of SMT inclusive of different interventional strategies and evolving treatment modalities. Grifols will analyze the use of COVID-19 specific, potentially disease modifying treatments for any potential differences between study arms. This analysis will be fully detailed in the SAP since medical understanding of COVID-19 interventions is rapidly evolving. For ethical reasons, there are no restrictions placed on what are perceived to be potentially life-saving therapies (apart from participation in another interventional clinical trial).

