#### **2.1.3 Exploratory Efficacy Objectives**

The exploratory objectives of the study are:

- To evaluate the effect of Liquid Alpha1-PI (Human) plus SMT versus placebo plus SMT with regard to quantitative severe acute respiratory syndrome, coronavirus 2 (SARS-CoV-2) viral load and anti-SARS-CoV-2 antibodies in hospitalized subjects with COVID-19.
- To evaluate whether Liquid Alpha1-PI (Human) plus SMT versus placebo plus SMT reduces the frequency of hyperinflammation based on a pre-specified biochemical definition through Day 29.
- To evaluate cytokine profile changes from baseline for Liquid Alpha1-PI (Human) plus SMT versus placebo plus SMT through Day 29.
- To evaluate levels of alpha1-proteinase inhibitor (alpha 1-PI, also known as alpha 1-antitrypsin [AAT]) activity and antigen through Day 29 (samples to be stored for measurement of both antigenic content and functional activity [potency] assays)

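### SAP 6.3 plans only per-arm summaries for viral load, antibodies, cytokines and hyperinflammation, although their objectives are worded against placebo and Protocol 9.1 calls for comparison between arms

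*SAP*

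**What the plan says.** **Objectives.** SAP 2.1.3 and Protocol 3.1.3 list four exploratory objectives, three of them comparative. The first asks about the effect of the product "plus SMT versus placebo plus SMT with regard to quantitative severe acute respiratory syndrome, coronavirus 2 (SARS-CoV-2) viral load and anti-SARS-CoV-2 antibodies". The second asks whether the product "plus SMT versus placebo plus SMT reduces the frequency of hyperinflammation based on a pre-specified biochemical definition through Day 29". The third begins "To evaluate cytokine profile changes from baseline for Liquid Alpha" and goes on to name placebo plus standard treatment as the comparator. The fourth, on alpha-1 antitrypsin (AAT), is only to evaluate levels and names no comparator.

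**Protocol method.** Protocol 9.1 states: "Secondary and exploratory efficacy analyses will be analyzed by means of Kaplan-Meier survival estimates and curves and compared between treatment groups". It then names the log-rank test for time-to-event variables, ANCOVA or ANOVA for normally distributed variables, and Wilcoxon otherwise. It leaves the detailed choice of method to the SAP.

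**SAP method.** For viral load, IgM/IgG and cytokines, SAP 6.3 says the change to Days 5±1, "15±1, and 29±1 will be summarized for each treatment group by visit". The hyperinflammation proportion will "be tabulated by treatment group. For this analysis, the denominator for calculating the proportion at each visit" and arm is the number of subjects with a lymphocyte count and at least two of the four other markers. For AAT, change in "activity and antigen to Days 8, 15, and 29 will be summarized for each treatment group by visit".

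**The concern.** Three objectives ask a between-arm question, and the protocol puts exploratory endpoints under between-arm methods. The SAP section that should carry this out stops at description within each arm.

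The choice does not look deliberate. SAP 7 says outright that safety will have no formal testing; SAP 6.3 has no such sentence. The SAP revision table records no decision to drop exploratory comparisons.

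These endpoints also bear on the proposed mechanism. Protocol 2.3.1 rests the rationale on suppression of pro-inflammatory cytokines and relief of the hyperinflammatory component. Markers may move in both arms through natural course and standard treatment, so the informative quantity is the randomised contrast. The plan never reports it.

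**Working it through.** **1. Is a contrast specified anywhere else?** SAP 4 gives general descriptive statistics, the two-sided 5% level and no multiplicity adjustment (4.5). The opening of SAP 6 adds the ITT population and says efficacy data are listed and tabulated. SAP 6.1 and 6.2 do compare arms, but only for primary and secondary endpoints. So none of the SAP 6.3 endpoints has a between-arm difference, CI, model or test.

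**2. What does Protocol 9.1 imply here?** None of the exploratory variables in Protocol 7.1.3 is time-to-event. For the continuous ones the applicable methods are ANCOVA, ANOVA or Wilcoxon. Protocol 9.1 names no test for a binary exploratory variable. For hyperinflammation, the mismatch is therefore with the objective and with the general statement that exploratory analyses are compared between groups.

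**3. What precision is at stake?** The plan states no figure for these endpoints, so there is none to reproduce. From the documents: about 100 subjects (SAP 9) randomised 1:1 (SAP 3.2.1), hence n = 50 per arm, and a two-sided 5% level (SAP 4), hence 1.96. Assumed: the same SD (set to 1) at baseline and follow-up, correlation ρ from 0.3 to 0.7, and all 50 per arm evaluable.

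- Variance of the difference in mean change: 2(1−ρ) × 2/n
- Variance of the ANCOVA difference: (1−ρ²) × 2/n
- Ratio: (1−ρ²) / [2(1−ρ)] = (1+ρ)/2
- Base half-width: 1.96 × √(2/50) = 0.392 SD

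| ρ | Variance ratio | Change-score 95% half-width, 0.392 × √(2(1−ρ)) | ANCOVA 95% half-width, 0.392 × √(1−ρ²) |
|---|---|---|---|
| 0.3 | 0.65 | 0.464 SD | 0.374 SD |
| 0.5 | 0.75 | 0.392 SD | 0.339 SD |
| 0.7 | 0.85 | 0.304 SD | 0.280 SD |

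With 40 evaluable per arm, multiply the half-widths by √(50/40) = 1.12; with 30, by √(50/30) = 1.29. For an assumed true difference of 0.5 SD, simulation (3,000 trials per setting, 50 per arm) gave power of 74%, 81% and 93% for ANCOVA at ρ = 0.3, 0.5 and 0.7, against 54%, 69% and 89% for change scores.

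**4. Hyperinflammation.** At assumed rates of 40% and 20% with 50 per arm, the large-sample half-width is 1.96 × √(0.4×0.6/50 + 0.2×0.8/50) = 0.175. The difference of −20 points would carry a CI of about −37.5 to −2.5. At a common assumed rate of 20%, 30% or 50% the half-width is about 16, 18 or 20 points. An exact interval would differ somewhat.

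**5. How many contrasts would be added?** With three post-baseline days each: viral load 3, IgM and IgG 6, seven cytokines 21, hyperinflammation 3. The total is 33. If tested unadjusted at 0.05 with no true effects, 33 × 0.05 = 1.65 false positives are expected. If independent, the chance of at least one is 1 − 0.95³³ = 82%.

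**The case against.** **The arms are tabulated side by side, so the comparison is available.** Largely true. A reader might infer that the report could say nothing about active versus placebo; the documents do not support that. Per-arm n, mean and SD of change, or proportions with a defined denominator, allow an unadjusted difference and CI to be rebuilt. What is missing is a reported contrast and the baseline adjustment, which the summary tables do not allow.

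**Protocol 9.1 leaves the method to the SAP.** It does, and it does not mandate ANCOVA or baseline adjustment. But discretion over which comparison to use does not plainly extend to replacing comparison with description without saying so.

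**With about 33 unadjusted contrasts, description is a defensible choice.** This has force. It argues for estimates with nominal intervals, clearly labelled, and against reading individual p-values. If description is the intention, SAP 6.3 should say so and give the reason.

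**AAT does not belong here.** Accepted. Its objective is not comparative, and since active subjects are infused with AAT, a contrast mainly checks exposure. Day 8 samples are also not required from discharged subjects who receive no second infusion (Protocol 4.2), so a Day 8 contrast would cover a subset selected after randomisation.

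**Conclusion.** The mismatch is real and modest. For viral load, IgM/IgG, cytokines and hyperinflammation, SAP 6.3 plans no between-arm estimate, while the objectives are comparative and Protocol 9.1 says exploratory analyses are compared between groups. Rebuilding the contrast from the planned tables costs precision: the ANCOVA to change-score variance ratio is about 0.65 to 0.85. That rests on assumed correlations of 0.3 to 0.7, equal SDs and 50 evaluable subjects per arm, none of which is a marker figure from the documents.

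A reader might also infer that the plan invites false positives by testing before-after change within each arm. It does not: SAP 6.3 specifies no within-arm test or p-value, so no such error rate follows from it.

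The effect is confined to how well the exploratory objectives can be interpreted. The primary analysis is untouched, and the futility list in SAP 8.2 contains no exploratory endpoint.

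**What to change.** In SAP 6.3, keep the per-arm summaries and add the following.

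- **Viral load, IgM, IgG and each cytokine, at Days 5, 15 and 29:** an ANCOVA on treatment and baseline value, log-transformed where skewed, reporting the LS-mean difference with nominal 95% CI. If non-normal, use Wilcoxon with the Hodges-Lehmann estimate and CI, as SAP 6.2 already does for ICU days. Fix the rule for choosing before unblinding.
- **Hyperinflammation at Days 5, 15 and 29:** the risk difference with exact unconditional 95% CI. Keep SAP 6.3's observed-data denominator; do not import SAP 6.1's rule that counts missing as an event. Show Day 1 as baseline only.
- **AAT:** leave descriptive as an exposure measure, or note that any Day 8 contrast covers a subset selected after randomisation.
- **Labelling:** mark every contrast exploratory and unadjusted for multiplicity, and show the number evaluable per arm at each visit.

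If the sponsor prefers description only, one sentence in SAP 6.3 should say so, give the reason and acknowledge the departure from Protocol 9.1. That reconciles the documents but leaves the comparative objectives without an estimate.

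The cost is a short SAP edit and some model output. It needs no new data, subjects or protocol amendment, since Protocol 9.1 already provides for comparison and leaves the method to the SAP. The downside is about 33 unadjusted contrasts, which the labelling has to make plain.
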